### **3. Problem statement**

Febrile Neutropenia (FN) is an important and serious health problem in children that receive chemotherapy because it increments the risk of major complications, it reduces the patient's quality of life, and increments treatment costs. Moreover, it is the most common diagnosis in children with cancer admitted into emergency rooms and the second cause of hospitalization, just after hospitalization for chemotherapy. In Mexico, FN incidence is 62% in children with solid tumors treated with cisplatin-based chemotherapy (CBC). Cisplatin is one of the most nephrotoxic drugs used in the clinic, this nephrotoxicity is showed by tubular damage that has electrolyte losses as a consequence, specially magnesium loss. Recently, an association between hypomagnesemia and the apparition of FN has been demonstrated. This finding can be explained based on the participation of magnesium as a cofactor in immune responses. Previous clinical trials, made in adult population, have showed that oral supplementation with magnesium in between chemotherapy cycles increment the serum concentration of magnesium and reduce hypomagnesemia episodes. With these evidences put together, we hypothesize that oral supplementation with magnesium oxide in between CBC cycles in children with solid tumors will maintain serum concentrations of magnesium in physiological parameters and in consequence this electrolyte will exercise its function in the immune system, contributing to the reduction of FN episodes. Therefore, the purpose of this protocol is to determine the efficacy of oral supplementation with magnesium to reduce incidence of febrile neutropenia in pediatric patients treated with cisplatin-based chemotherapy.

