#### **5. Objectives**

*General:*

- Determine the efficacy of oral supplementation with magnesium to reduce febrile neutropenia episodes in pediatric patients treated with cisplatin-based chemotherapy

*Specific:*

- Recruit patients for the clinical trial until completion of the sample size
- Monitor clinical accomplish of patients to magnesium supplementation
- Build and analyze the data base

*Secondary:*

- Determine if supplementation with magnesium oxide modifies the time of apparition of febrile neutropenia in pediatric patients treated with cisplatin-based chemotherapy
- Evaluate the safety of supplementation with magnesium oxide
- Determine the efficacy of oral supplementation with magnesium oxide to reduce incidence of hypomagnesemia in pediatric patients treated with cisplatin-based chemotherapy

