### *Procedure*

Basal status of trial will be integrated at the moment the attending physician indicates that the patient will be treated with cisplatin-based chemotherapy (CBC). The clinical monitor will establish contact with the parent of the patient and explain the purpose of the trial and will invite them to participate through signing the informed consent. Once the informed consent is signed the clinical monitor will explain the patient the purpose of the trial in order to obtain the informed assent.

To prove the hypothesis, it is required to randomize 107 CBC cycles to the intervention group and 107 CBC cycles to the control group. To determine whether the patient will receive supplementation or not in that CBC cycle, the clinical monitor will notify the principal investigator that a patient will commence treatment. In response the investigator will communicate the clinical monitor where to allocate the patient's CBC cycle. Randomize will be made by generating non-repeated random numbers with the program available at: <http://randomnumbregenerator.intemodino.com/es/generador-de-numeros-aleatorios.html>.

Patients assigned to the supplementation group will receive institutional care protocol plus a bottle with magnesium oxide tablets and will be explained that they should take a tablet daily. In the case that the patients were assigned to the control group they will receive institutional care protocol only.

Oral supplementation with magnesium consists on a daily tablet (245 mg magnesium oxide and 5mg magnesium gluconate, GNC, US). Supplementation will be interrupted when the patients returns for the administration of another cisplatin cycle or with the appearance of a febrile neutropenia episode. In the same sense, patients on control group will be monitored until an FN episode appears or until they return for the next cisplatin cycle.

The main outcome of this study is the apparition of febrile neutropenia that is defined as a neutrophils total count below  $1000/\text{mm}^3$  together with a unique temperature  $>38.3\text{ }^\circ\text{C}$  or a sustained temperature of  $\geq 38\text{ }^\circ\text{C}$  for over an hour. Patients with a neutrophils total count  $<100/\text{mm}^3$  will be considerate as a profound neutropenia. Clinical monitor will visit the emergency department every day to identify if one of the enrolled patients has been hospitalized due febrile neutropenia diagnosis.

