To evaluate if oral supplementation with magnesium reduces secondary to CBC hypomagnesemia's, serum magnesium will be quantified before CBC and it will be measured again after the apparition of febrile neutropenia or at the moment the patients returns to another CBC cycle. Serum concentrations of magnesium below  $1.6\text{ mg/dL}$  will be considered as hypomagnesemia.

Daily maximum intake of magnesium supplements recommended for children over 9 years is  $350\text{ mg}$ . Nevertheless, the dose that will be used on this protocol is less that the recommended, it is necessary to evaluate safety of supplementation with magnesium in pediatric patients with cancer. To fulfill this purpose, each patient will be given a binnacle where they will register adverse effects that could be presented, such as diarrhea, nausea, vomit, etc.; binnacle is showed in Appendix 1. Moreover, clinical studies like hematic biometry, and other biochemical tests will be performed to determine if there is hepatotoxicity (ALT, AST and alkaline phosphatase), nephrotoxicity (creatinine) and cardiotoxicity (LDH). Biochemical determination will be made on both groups at the basal status and before every CBC cycle. Oral supplementation with magnesium will be interrupted in patients that present severe adverse reactions. All adverse reactions will be registered according NOM-220-SSA1-2015.

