### Biochemical Tests

Parameter	Measure before supplementation	Date	Measure after supplementation	Date
Leukocytes/mm 				
Neutrophils/mm 				
Platelets/mm 				
Hb (g/dL)				
Hto (%)				
Magnesium (mg/dL)				
Calcium (mg/dL)				
ALT (U/L)				
AST (U/L)				
Alkaline phosphatase (U/L)				
Creatinine (mg/dL)				
LDH (U/L)				

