**Febrile neutropenia**

Apparition Date \_\_\_\_\_ Hospitalization (S/N) \_\_\_\_\_

Hospitalization Days \_\_\_\_\_ Discharge Date \_\_\_\_\_

Microbiology results \_\_\_\_\_

Treatment \_\_\_\_\_

Complications \_\_\_\_\_

Febrile neutropenia prophylaxis received \_\_\_\_\_

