**Comments:**

Done by: \_\_\_\_\_

## Appendix 3

*Operability of variables*

Variable	Definitions
Fever and neutropenia Units: With or without febrile neutropenia	Conceptual Definition: adverse reaction to chemotherapy that manifests with fever and neutrophil count below normal limits. Operative Definition: count < 1000 neutrophils/mm  and a temperature > 38.3 °C or a sustained temperature ≥ 38 °C over the course of an hour. Variable type: Dichotomous qualitative.
Hypomagnesemia Units: With or without hypomagnesemia	Conceptual Definition: adverse reaction to chemotherapy characterized by low serum magnesium levels. Operative Definition: Serum concentrations of magnesium ≤ 1.6 mg/dL. Variable type: Dichotomous qualitative.
Serum magnesium levels Units: mg/dL	Conceptual Definition: Quantity of magnesium in serum. Operative Definition: Quantity will be measured on patient's serum before and after supplementation with magnesium. Variable type: Continuous quantitative.
Age Units: years old	Conceptual Definition: Time passed since birth until start date of supplementation with magnesium. Operative Definition: Calculated with birthdate and start date of supplementation with magnesium. Variable type: Discrete quantitative.
Gender Units: male or female	Conceptual Definition: Biological conditions distinguishing between males and females. Operative Definition: Gender registered on capture sheets. Variable type: Dichotomous qualitative.
Diagnosis Units: type of solid tumor.	Conceptual Definition: Procedures performed by attending oncology physicians to determine type of tumor. Operative Definition: Diagnosis registered on capture sheets. Variable type: Ordinal qualitative.
Height Units: centimeters.	Conceptual Definition: Human height. Operative Definition: Height registered according to nursery sheets before any CBC cycle Variable type: Continuous quantitative.
Weight Units: kilograms.	Conceptual Definition: Corporal mass measure. Operative Definition: Weight registered according to nursery sheets before any CBC cycle. Variable type: Continuous quantitative.

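### The second magnesium sample is timed by whether febrile neutropenia occurs, so the hypomagnesaemia comparison between arms can partly reflect when blood was drawn

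*Combined protocol and SAP*

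**What the plan says.** Section 6 (Procedure) has magnesium measured before cisplatin-based chemotherapy (CBC). Of the second sample it says that "it will be measured again after the apparition of febrile neutropenia or at the moment the patients returns to another CBC cycle". An FN cycle is therefore sampled after FN appears, and an FN-free cycle on return.

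The endpoint is a stated secondary objective (section 5): "Determine the efficacy of oral supplementation with magnesium oxide to reduce incidence of hypomagnesemia". It is also the step through which section 3 expects benefit: supplementation "will maintain serum concentrations of magnesium in physiological parameters and in consequence this electrolyte will exercise its function in the immune system".

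Exposure ends at the same two moments: "Supplementation will be interrupted when the patients returns for the administration of another cisplatin cycle or with the appearance of a febrile neutropenia episode".

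The capture sheet (Appendix 2, Biochemical Tests) has one dated post-baseline column, "Measure after supplementation". It also records the CBC start date and, for FN, the "Apparition Date". Appendix 3 defines the variable by measurement in "serum before and after supplementation with magnesium", with no fixed day. Section 7 gives no rule for sampling time or FN status when magnesium is analysed.

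A further statement bears on the remedy: "Biochemical determination will be made on both groups at the basal status and before every CBC cycle". The safety tests listed just before it do not name magnesium, although magnesium is a row in the capture-sheet panel.

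**The concern.** Randomisation makes the arms comparable if the endpoint is measured the same way in both. Here the occasion depends on a post-randomisation event that the supplement is meant to make rarer. If the trial succeeds on FN as planned, the control arm will have more samples taken at FN and the supplemented arm more taken at return. Any systematic change in magnesium between the two occasions then enters the arm comparison.

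A second route does not need different FN rates. Supplementation stops at FN, and only one arm is supplemented, so the change from FN to return may itself differ by arm.

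At stake is the reading of the mechanism. Readers will use the hypomagnesaemia result to judge whether any FN effect is explained by magnesium.

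**Working it through.** **Inputs from the documents.** FN 62% in control and 42% in the supplemented arm, two-sided alpha 0.05, beta 0.20, 107 cycles per arm (section 7, Sample Size Calculation). Hypomagnesaemia incidence around 40% in children given cisplatin (section 2), a general figure used here only to centre the illustration.

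**Assumed.** The change in prevalence between the two occasions, which the documents do not give.

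**The plan's own figure.** The two-proportion formula gives 97 per arm without the continuity correction and 107 with it. The stated 107 is reproduced, and nothing below alters it.

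**Sampling mix at the planned FN rates.**
- Control: 0.62 × 107 ≈ 66 samples at FN, 0.38 × 107 ≈ 41 at return.
- Supplemented: 0.42 × 107 ≈ 45 at FN, 0.58 × 107 ≈ 62 at return.

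**Formula.** In one arm, let q be the prevalence of low magnesium at return over all cycles. Let d be the prevalence at the FN-time sample minus that at return, in the same FN cycles. Then:

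observed prevalence = q + P(FN) × d

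The observed arm difference is the return-occasion difference plus

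bias = P(FN, control) × d(control) − P(FN, supplemented) × d(supplemented)

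This is zero if d is zero in both arms, or if FN rates and d are both equal across arms.

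**Equal d, no true magnesium effect (q = 40% in both arms).** Bias = (0.62 − 0.42) × d = 0.20 × d.

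| Assumed d | Control | Supplemented | Artefact | Two-sided rejection |
|---|---|---|---|---|
| 0 | 40.0% | 40.0% | 0 | 5% |
| +20 points | 0.40 + 0.62 × 0.20 = 52.4% | 0.40 + 0.42 × 0.20 = 48.4% | +4 points | 9.0% |
| −20 points | 0.40 − 0.62 × 0.20 = 27.6% | 0.40 − 0.42 × 0.20 = 31.6% | −4 points | 9.8% |

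The rejection rates use a normal approximation with 107 independent cycles per arm. Exact binomial calculation with the 95% interval for the relative risk gives 8.6% and 9.2%. With FN at 62% versus 52%, the artefact is 0.10 × 0.20 = 2 points and rejection is 6.0% to 6.2%.

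**Scale.** The 95% half-width for a difference near 40% is 1.96 × √(2 × 0.4 × 0.6 / 107) = 0.131, about 13 points.

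**Unequal d (assumed values).**
- 20 points in control, 10 in supplemented: 0.62 × 0.20 − 0.42 × 0.10 = +8.2 points.
- 10 points in control, 20 in supplemented: 0.62 × 0.10 − 0.42 × 0.20 = −2.2 points.

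**The case against.** **The planned value is a coherent end-of-exposure measure.** The sample is taken when supplementation ends, and section 3 concerns magnesium during the interval between cycles. A return sample in an FN cycle is off supplement. If the effect is wholly lost after stopping and otherwise equal across cycles, only 1 − 0.42 = 58% of it would remain at the planned FN rate.

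An assumed example shows the planned value doing better. Let 40% versus 30% be low before FN, with FN risk 90% if low and 43.3% if normal, and let 20% be low at return in both arms. Control FN is 0.40 × 0.90 + 0.60 × 0.433 = 62%, and supplemented FN is 0.30 × 0.90 + 0.70 × 0.433 = 57.3%. The planned rule reads 0.36 + 0.38 × 0.20 = 43.6% versus 0.27 + 0.427 × 0.20 = 35.5%. That 8.1-point difference is close to the true 10 points before FN, while the return comparison shows none. This objection stands: the return comparison should accompany the planned one, not replace it.

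**Later values will exist for some FN cycles.** Magnesium is measured before CBC, so a child who re-enters after an FN cycle supplies a return value for it, and the dates show which occasion each sample came from. A reader might infer that the data can never address the problem; that goes too far. But the plan does not assign the later value to the preceding cycle, and the value may be available only for children who re-enter. Hypomagnesaemia before CBC is a bar to inclusion, so re-entry may itself select on magnesium. Splitting samples by FN status conditions on a post-randomisation outcome and is not a clean correction.

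**The false-positive figure needs a particular scenario.** It requires FN to fall by 20 points with no magnesium effect, which is not the mechanism in section 3. If supplementation acts on FN only through magnesium and d is equal across arms, no magnesium effect means no FN difference and no bias. That also stands, and it limits the severity.

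**Conclusion.** The point holds as a minor to moderate one, confined to a secondary objective. Sampling time depends on the primary outcome, and the plan has no comparison at a common occasion. The documents support neither a size nor a direction for the bias. The 4-point artefact and 9–10% rejection rate rest on an assumed equal 20-point change, the planned FN difference, no true magnesium effect, and cycles treated as independent.

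Three stronger readings are not supported:
- **That the hypomagnesaemia result will be biased.** If magnesium does not change between the two occasions in either arm, there is no bias.
- **That the distortion has a small fixed ceiling.** Such a limit needs the change to be equal in both arms and FN risk to follow prevalence at return. Both are doubtful when supplementation stops at FN.
- **That a higher prevalence in FN-time samples would prove bias.** Section 2 reports an association between low magnesium and FN, so a higher prevalence is expected without any timing effect.

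The FN comparison and its 107 cycles per arm are untouched.

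**What to change.** 1. State that magnesium is measured at the pre-CBC draw on return for every randomised cycle that has a next CBC cycle, with or without FN and whether or not the child is randomised again. Record it in a capture-sheet field separate from the FN-time value.
2. Keep the FN-or-return value as the end-of-supplementation analysis, labelled as having outcome-dependent timing.
3. Pre-specify an arm comparison at the common return occasion, and adjust both analyses for the index-cycle pre-CBC magnesium.
4. Report by arm the days from CBC start to sample, since return is a common occasion but not a fixed day, and the number of cycles with no next CBC cycle.
5. Claim an effect on hypomagnesaemia only with both results shown.

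**Cost.** One extra field and one extra analysis. Biochemistry is already scheduled before every CBC cycle, so no visit is added. The return contrast may be diluted, because FN cycles are off supplement by then, and it omits cycles with no next CBC cycle. Under the present rule a last cycle without FN has no second value either, so the additional loss is last cycles with FN, which remain in the end-of-supplementation analysis.

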### **Cancer treatment**

Cancer treatment options depends on cancer type, stage, and other factor such as age, and general health status of each patient. Treatment is founded in three major strategies: surgery, radiotherapy and chemotherapy. Chemotherapeutic drugs work causing cellular death in diverse ways. Genotoxic agents are drugs that damage DNA, interfere with DNA replication, stop cellular division or induce cellular apoptosis. However, chemotherapeutic drugs also affect non-cancerous cells, contributing to their toxicity. Fast regenerating cells, like the ones from the bone marrow and the walls of the intestines, tend to be more affected, causing neutropenia and mucositis, respectively. Thus, the death of non-cancerous cells constitutes the most frequent adverse reaction of chemotherapy. About 75% of pediatric patients with cancer had suffered at least one adverse reaction associated to chemotherapy,

and 36% had suffered a severe adverse reaction that threatens their life or permanently incapacitates them.

Cisplatin is an irreplaceable drug in the treatment of diverse solid tumors in both adults and children. At the Hospital Infantil de México Federico Gómez, chemotherapeutic schemes that include cisplatin as a first line treatment for solid tumors like osteosarcomas, hepatoblastomas and germ cells tumors.

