### **Safety of magnesium supplementation**

Adverse effects of magnesium caused by ingestion of food hadn't been identified since kidneys have mechanisms for the elimination of magnesium surplus. Nonetheless, adverse effects of magnesium secondary to the ingestion of supplements had been showed. The first symptoms of magnesium surplus are diarrhea and laxative effects that originates on the osmotic activity of non-absorbed salts in the intestine and colon, as well as gastric motility stimulation (these adverse effects are the reason why magnesium salts are used as laxative therapy). Magnesium salts that were reported for diarrhea are carbonate, chloride, gluconate and magnesium oxide.

Toxicity symptoms of magnesium surplus manifests when serum concentrations are above 4.2 mg/dL; and can include hypotension, nausea, vomit, facial blush, urine retention, ileus, depression and lethargy before it progresses to muscular weakness, dyspnea, extreme hypotension, irregular heart rhythm and cardiac arrest.

Individuals with renal impair are in major risks to present adverse effects secondary to magnesium supplementation. Symptoms of toxicity induced by magnesium had been observed in patients with renal impair that consumed moderate doses of magnesium laxatives or antacids.

Within clinical trials designed specifically to reduce incidence of hypomagnesemia induced by cisplatin using any magnesium salt it has been described the presence of vomit and diarrhea. However, one of the trials showed no gastrointestinal toxicity.

The Food and Nutrition Board of the US (FNB) established a maximum daily limit for magnesium supplementation in children: from 1 to 3 years, 65mg per day; from 4 to 8 years, 110 mg per day; and in children >9 years, 350 mg per day.

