### *Sample Size Calculation*

Necessary number of patients was estimated considering a normal distribution means two proportions formula, using  $\alpha = 0.05$  (two tails),  $\beta = 0.20$ , 1 on 1 proportion of assignment to each group. For calculus it was considered that non-exposed group will have a proportion of 62%, while supplemented group will have a proportion of 42% (delta

20%). With the previous conditions and considering a continuity correction, to perform the study it is required to randomize 214 cycles and assign 107 to control group and 107 to supplemented group. Calculus was done with Sample Size Calculator for Designing Clinical Research by University of California San Francisco, available at <http://www.sample-size.net/sample-size-proportions/>.

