**HOSPITAL INFANTIL DE MÉXICO FEDERICO GÓMEZ**  
**FACULTAD DE ESTUDIOS SUPERIORES ZARAGOZA**

### Daily binnacle of symptoms

Folio \_\_\_\_\_ Delivery of binnacle \_\_\_\_\_

Symptoms	Start Date	Due Date
Constipation		
Diarrhea		
Gas or abdominal distension		
Dizziness		
Nervousness		
Abdominal pain		
Blisters		
Rash		
Itchiness		
Urticaria		
Swelling of eyes, face, lips, tongue, throat, arms, hands, legs, feet, ankles or calfs		
Difficulty breathing or swallowing		
Indigestion		
Excessive fatigue		
Pain on the upper right abdomen		
Nausea		
Loss of appetite		
Yellowing on the skin and eyes		
Flu symptoms		
Paleness		
Fast heartbeat		
Weightloss		
Back pain		
Difficulty or pain to urinate		
Blurry vision, changes on color perception and other visual problems		
Red eyes		
Neck stiffness		
Headache		
Confussion		
Other		

Reception: \_\_\_\_\_

## Appendix 2

HOSPITAL INFANTIL DE MÉXICO FEDERICO GÓMEZ  
FACULTAD DE ESTUDIOS SUPERIORES ZARAGOZA

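### LDH alone cannot support a cardiotoxicity conclusion, and the symptom diary does not prompt for several magnesium-excess signs that the protocol itself names

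*Combined protocol and SAP*

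**What the plan says.** Section 5 makes safety of magnesium oxide a secondary objective. Section 6 (Procedure) carries this out in three ways.

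- **Laboratory tests.** Blood tests are to establish whether liver, kidney or heart toxicity is present. The kidney and heart entries read "nephrotoxicity (creatinine) and cardiotoxicity (LDH"). Sampling is at baseline and before every cisplatin cycle, in both groups.
- **Diary.** Each patient gets a symptom diary in which "they will register adverse effects that could be presented, such as diarrhea, nausea, vomit, etc.; binnacle is showed in Appendix 1".
- **Registration.** All adverse reactions are to be registered under the national pharmacovigilance standard.

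Section 2 (Safety of magnesium supplementation) says that toxicity appears above a serum level of 4.2 mg/dL. It lists early signs and then a progression: "lethargy before it progresses to muscular weakness, dyspnea, extreme hypotension, irregular heart rhythm and cardiac arrest".

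The only heart-related row in the Appendix 1 diary is "Fast heartbeat". The Appendix 2 capture sheet records LDH in U/L and serum magnesium before and after supplementation. It has no field for blood pressure, pulse or ECG.

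**The concern.** Two things do not fit together. First, the test assigned to the heart does not measure the heart effects that the protocol attributes to magnesium excess. The patients have "solid tumors like osteosarcomas, hepatoblastomas and germ cells tumors", and the capture sheet allows for anthracyclines, so LDH may move for reasons unrelated to the heart. Secondly, the diary does not follow either the list of signs in section 2 or the description of the diary in section 6.

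At stake is what can be said on a stated secondary objective. A sentence in the report that supplementation did, or did not, show cardiotoxicity would rest on a measurement that cannot bear it. For the unprompted signs, a comparison between arms would depend on what families choose to write down. The trial is open-label, so families know the allocation, and volunteered entries may differ by arm for that reason alone. The protocol does not treat the risk as remote: section 2 says that renal impairment raises the risk of magnesium adverse effects and also that cisplatin is highly nephrotoxic.

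**Working it through.** The plan gives no figure on this point, so the check is a comparison of sections.

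**Step 1: LDH against the named cardiovascular effects.** Section 2 names hypotension, irregular rhythm and cardiac arrest. LDH is an enzyme concentration in blood, drawn at baseline and before each cycle. It records neither pressure nor rhythm at any time. A normal value therefore does not exclude the named effects, and a raised value does not show them. No LDH cut-off appears in section 6, section 7 or Appendix 3. Appendix 3 defines no cardiotoxicity variable, and section 7 describes no safety analysis.

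**Step 2: signs in section 2 against the 30 rows of Appendix 1** (the last row being Other). Hypotension is counted once, which gives 12 signs.

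| Sign in section 2 | Diary row | Match |
|---|---|---|
| Nausea | nausea | direct |
| Dyspnea | breathing or swallowing difficulty | direct |
| Urine retention | trouble urinating | near-direct |
| Hypotension | dizziness | indirect |
| Ileus | constipation, distension | indirect |
| Lethargy | fatigue | indirect |
| Irregular rhythm | fast heartbeat | indirect |
| Vomiting | none | Other only |
| Facial flushing | none | Other only |
| Depression | none | Other only |
| Muscle weakness | none | Other only |
| Cardiac arrest | not a diary item | – |

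The count is 3 direct or near-direct + 4 indirect + 4 with no row + 1 not applicable = 12. If indirect rows are accepted, 4 of 12 signs lack a prompt. If they are not, 4 + 4 = 8 of 12 do.

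**Step 3: section 6 against Appendix 1.** Section 6 gives vomiting as an example of what the diary records. Appendix 1 has a nausea row but no vomiting row. This is a plain contradiction, and section 2 reports vomiting and diarrhea in earlier trials of magnesium with cisplatin. Diarrhea does have a row.

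**Step 4: what else would capture these signs.** Serum magnesium is measured before the cycle and again at febrile neutropenia or at return. Its stated purpose in section 6 is to assess hypomagnesemia. Appendix 3 defines a low category and a continuous level but no high one. The second sample comes late in the cycle, so an earlier peak could be missed. Appendix 2 has an open table for adverse effects (headed as effects of chemotherapy) and a comments field.

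**Step 5: effect of five added rows** (vomiting, flushing, muscle weakness, low mood, irregular heartbeat). Direct or near-direct matches rise from 3 to 8. Three remain indirect (hypotension, ileus, lethargy), none is without a row, and cardiac arrest stays outside the diary: 8 + 3 + 0 + 1 = 12.

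**The case against.** The strongest reply is that the most direct check on magnesium excess is serum magnesium, which is collected in both arms and can be set against the 4.2 mg/dL in section 2. The diary has an open row and several near-equivalents, Appendix 2 has an open adverse-effect table, and all adverse reactions are to be registered. LDH is measured in the control arm too, so tumour- or chemotherapy-driven changes should balance in expectation. They add noise but do not by themselves create a false effect of the supplement. Which symptoms to pre-list is partly a matter of judgement.

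Most of this stands, and it rules out two stronger readings. A reader might infer that the plan would miss magnesium toxicity altogether. The documents do not support that, because the routes above exist; the signs are not systematically prompted, which is less than being missed. A reader might also infer that every cycle would receive an LDH-based cardiac classification, or that the supplement would be falsely blamed. With no cut-off, no cardiotoxicity variable and no safety analysis, nothing in the plan produces such a classification, and the control arm guards against false attribution.

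What the reply does not answer is that section 6 still sets out to determine cardiotoxicity from LDH alone, that balance between arms does not make LDH a measure of rhythm or pressure, and that the diary contradicts section 6 on vomiting.

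**Conclusion.** The point holds in limited form. LDH is the only test assigned to the heart, and it cannot support a cardiac safety conclusion in either direction. The diary lacks a row for 4 of the 12 signs named in section 2, including vomiting, which section 6 says it records; another 4 have only an indirect row. The primary outcome, its analysis and the sample size of 107 cycles per arm are untouched. The change is worth making before diaries are issued, because symptoms that were not asked about cannot be reliably recovered later.

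The conclusion rests on two judgements. The matching of rows to signs is mine, and the range of 4 to 8 shows how far it could move. That LDH is non-specific for the heart is general knowledge, not a statement in the protocol; the argument in step 1, that an enzyme level does not record pressure or rhythm, does not need it.

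**What to change.** 1. **Section 6.** Remove the cardiotoxicity label from LDH. Report LDH by arm as a laboratory change only, and draw no cardiac conclusion from it.
2. **Appendix 1.** Add prompted rows for vomiting, facial flushing, muscle weakness, low mood and irregular heartbeat, on the same form in both arms.
3. **Section 7 and Appendix 3.** Define post-cycle serum magnesium as a safety variable. Report it by arm, with the number of values above the 4.2 mg/dL in section 2. This is a reporting count, not a rule for managing patients. State that the sample is taken only at febrile neutropenia or at return and may miss an earlier peak.

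Transcribing routine heart rate and blood pressure to Appendix 2 is optional. Their availability is an assumption, since Appendix 3 cites nursing sheets only for height and weight. Readings at presentation with febrile neutropenia would be affected by the fever and would exist only for cycles with the primary outcome.

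The cost is small: wording, five diary rows and one table, with no new blood sample. The protocol gives up a stated cardiotoxicity assessment, and the diary becomes slightly longer.
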